3.4.1.3 Key Secondary Analysis: Responders

A number of response criteria have been defined:

- $\geq 5\%$ absolute reduction in LFC as measured by MRI-PDFF from baseline to Week 12/ET;
- $\geq 10\%$ absolute reduction in LFC as measured by MRI-PDFF from baseline to Week 12/ET;
- $\geq 20\%$ absolute reduction in LFC as measured by MRI-PDFF from baseline to Week 12/ET;
- Relative reduction in LFC $\geq 20\%$ as measured by MRI-PDFF at Week 12/ET;
- Relative reduction in LFC $\geq 30\%$ as measured by MRI-PDFF at Week 12/ET;

For each response criteria, the number and percentage of responders will be summarized by treatment group for the ITT Population; patients without a Week 12/ET MRI-PDFF assessment will be imputed as non-responders.

Each response criteria will be analyzed by a Cochran-Mantel-Haenszel test, stratified by statin use and T2DM status at screening for Part A, stratified by statin use and LFC stratification category for Part B. The responder analysis will be repeated using logistic regression models adjusting for treatment (pooled EYP001a and placebo for Part A, each EYP001a group and placebo for Part B), statin use and T2DM at screening for Part A, statin use stratification category for Part B, and baseline LFC. Note for Part B the baseline LFC is included as a covariate, and so the LFC stratification factor will not be included in the logistic regression model. The Cochran-Mantel-Haenszel test p-value will be reported. From the logistic regression, the odds ratio, two-sided 95% CI, and p-values will be reported.

3.4.1.4 Key Secondary Analysis: Percent Change

The main analysis of percent change from baseline will be performed on the ITT Population. As for the primary analysis, missing MRI-PDFF values at Week 12/ET will be imputed based on the missing at random assumption using multiple imputation.

The percent change from baseline to Week 12/ET in LFC will be analyzed for the ITT Population in similar ANCOVA model as described for the primary analysis. The analysis will be repeated as sensitivity analyses for the mITT and Per-Protocol Populations.

3.4.1.5 Key Secondary Analysis: cT1

The main analysis of change and percent change from baseline in cT1 will be performed on the ITT Population. As for the primary analysis, missing cT1 values at Week 12/ET will be imputed based on the missing at random assumption using multiple imputation. Missing baseline cT1 will not be imputed. Patients with missing baseline cT1 will not be included in the analysis.

The change and percent change from baseline to Week 12/ET in cT1 will be analyzed for the ITT Population using similar ANCOVA models to that described for the primary analysis, although baseline LFC covariate will be replaced with baseline cT1, and LFC stratification group (Part B) will be included as a factor. The analysis will be repeated as sensitivity analyses for the mITT and Per-Protocol Populations.

3.4.2 Analysis of Other Efficacy Endpoints

All other secondary efficacy endpoints will be summarized and analyzed based on the ITT Population. Descriptive statistics of the baseline, visit value and change from baseline to each post-baseline visit will be presented by treatment group for each secondary efficacy parameter. Percent change from baseline may be included where applicable.

3.4.2.1 Biomarkers of Liver Fibrosis and Inflammation

The change from baseline in the available biomarkers of liver fibrosis and inflammation at each analysis visit, as appropriate, will be analyzed using a mixed-model repeated measures (MMRM). The factors in the model will be treatment group (pooled EYP001a and placebo for Part A, each EYP001a group and placebo for Part B), stratification factors – statin use and T2DM status at screening for Part A or statin use and LFC stratification category for Part B, baseline value, visit and the treatment-by-visit interaction. An unstructured covariance matrix will be used (TYPE=UN). The LSMeans for change from baseline at each post-baseline visit will be estimated and compared between the treatment groups.

For Part B, non-parametric analysis will be used for hs-CRP. An unstratified Wilcoxon based analysis will be performed and the Hodges-Lehmann estimate along its 95% confidence intervals will also be provided.

The formulas for the derived noninvasive biomarkers will be documented in separate specifications. The derived noninvasive biomarkers, including ELF, will be summarized only. No formal statistical analysis will be conducted.

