2.2 Secondary Objectives

The secondary objectives are the following:

- To explore the PK of EYP001a
- To evaluate PD effects of EYP001a on bile acid-related markers as appropriate
- To assess the effects of EYP001a on lipid and metabolic profiles
- To assess the safety of EYP001a with statin coadministration
- To assess the effects of EYP001a on noninvasive biomarkers of liver fibrosis and inflammation

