7.1.2 Secondary Efficacy Variables

The secondary efficacy variables include the following:

- Proportion of patients with $\geq 5\%$ absolute reduction in LFC as measured by MRI-PDFF from baseline to Week 12
- Proportion of patients with $\geq 10\%$ absolute reduction in LFC as measured by MRI-PDFF at Week 12
- Proportion of patients with $\geq 20\%$ absolute reduction in LFC as measured by MRI-PDFF at Week 12
- Proportion of patients with a relative reduction in LFC $\geq 20\%$ as measured by MRI-PDFF at Week 12
- Proportion of patients with a relative reduction in LFC $\geq 30\%$ as measured by MRI-PDFF at Week 12
- Percent change (relative reduction) in LFC as measured by MRI-PDFF from baseline to Week 12
- Change and percent change in imaging-derived mean cT1 from baseline to Week 12
- Change and percent change in WHR from baseline to Week 12 (Part B only)
- Change and percent change in WHtR from baseline to Week 12 (Part B only)
- Change in the following biomarkers of liver fibrosis and inflammation: ALT, AST, AST/ALT ratio, adiponectin, high sensitivity C-reactive protein, interleukin 6, tumor necrosis factor alpha, cytokeratin-18, fibronectin, hyaluronic acid, procollagen type III N-terminal peptide, tissue inhibitor of metalloproteinases-1 (and derived enhanced liver fibrosis score), Pro-C3, and chitinase-3-like protein 1 (also known as YKL-40) from baseline to Week 4, Week 8, and Week 14/ET, as applicable

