10.2.1.3 Secondary efficacy analysis

The statistical analysis of secondary efficacy variables based on change from baseline to Week 12 will be conducted with a similar ANCOVA model, while secondary efficacy variables measured at multiple timepoints will be analyzed by mixed effect model repeated measures model.

The responder (categorical) variables will be analyzed by a Cochran-Mantel-Haenszel test, stratified by statin comedication use and T2DM status at screening in Part A and statin comedication and LFC at screening in Part B. The analysis of the responder variables will be repeated using logistic regression models, adjusting for treatment, statin comedication at screening, and T2DM status at screening. Patients without a Week 12 or end of treatment MRI-PDFF assessment will be imputed as nonresponders. All secondary efficacy variables will be summarized using descriptive statistics.

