2.1.2 Secondary Objectives and Endpoints

Secondary Objective	Endpoint
To explore the pharmacokinetics (PK) of EYP001a	EYP001a concentrations
To evaluate pharmacodynamic (PD) effects of EYP001a on bile acid-related markers as appropriate	Plasma levels of: 
• 7a-hydroxy-4-cholest-3-one;• fibroblast growth factor 19;• and total, primary, and secondary bile acids (such as
◦ chenodeoxycholic acid,◦ deoxycholic acid,◦ lithocholic acid,◦ and/or others as appropriate).
To assess the effects of EYP001a on lipid and metabolic profiles	
• Branched-chain amino acid concentrations• Hemoglobin A1c (HbA1c)• Homeostatic model assessment for insulin resistance (morning fasting glucose and insulin)• Lipoprotein insulin resistance index by nuclear magnetic resonance based on serum
◦ cholesterol,◦ high-density lipoprotein cholesterol,◦ low-density lipoprotein (LDL) cholesterol,◦ triglycerides,◦ apolipoprotein B,◦ small dense-LDL, and◦ lipoprotein(a)• Lipoprotein particle size• Small LDL particle number• Small very low-density lipoprotein (VLDL) particle number• VLDL size
To assess the safety of EYP001a with statin coadministration	Safety and tolerability assessments will include the monitoring of

Secondary Objective	Endpoint
	
adverse events (AEs);AEs of special interest (AESIs) (i.e.,
pruritus [Part A only],drug-induced liver injury [Part A only],elevation of transaminases [Part B only],andall muscle-related AEs);serious AEs (SAEs); and findings fromphysical examinations,vital signs,electrocardiograms (ECGs), andclinical laboratory parameters.
To assess the effects of EYP001a on noninvasive biomarkers of liver fibrosis and inflammation	
Change from baseline to Week 4, Week 8, and Week 14/ET, as applicable, in the following biomarkers of liver fibrosis and inflammation:
 
Alanine aminotransferase (ALT),Aspartate aminotransferase (AST),AST/ALT ratio,adiponectin,high sensitivity C-reactive protein (hs-CRP),interleukin 6,tumor necrosis factor alpha,cytokeratin-18,fibronectin,hyaluronic acid,procollagen type III N-terminal peptide,tissue inhibitor of metalloproteinases-1 (and derived enhanced liver fibrosis [ELF] score),Pro-C3, andchitinase-3-like protein 1 (also known as YKL-40)

Additional secondary efficacy variables include the following:

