5 CHANGES FROM PROTOCOL-SPECIFIED STATISTICAL ANALYSES

For Part B analysis of LFC as measured by MRI-PDFF, the ANCOVA model specified in the Protocol includes both baseline LFC as a covariate and LFC stratification (3 categories) as a factor. Since this is redundant information, LFC stratification as a factor will be dropped as a covariate from the model; baseline LFC as a covariate is sufficient.

After Part A analysis was completed, the Per-Protocol Population definition was updated to require subjects to finish the 12-week Treatment Period. However, this part of the definition is excluded for analysis. Instead, the Part B Per-Protocol Population is clarified to require $\geq 60\%$ study drug compliance.

There are some other minor changes from the protocol-specified statistical analyses detailed in this SAP:

- Week 12 included for biomarkers of liver fibrosis and inflammation, as appropriate;
- Study endpoints and definition of mITT Population updated to clearly allow patients with ET assessments (not just Week 12 assessments) to be included.
- HbA1c is not analyzed at Week 2 and Week 12 with the other lipid and metabolic profile parameters.

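### SAP 3.4.2.1 makes the ELF score descriptive only, although the protocol assigns it a repeated-measures analysis, and SAP Section 5 does not declare the change

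*SAP*

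**What the plan says.** **Protocol.** The fifth secondary objective (Section 2.2) is: "To assess the effects of EYP001a on noninvasive biomarkers of liver fibrosis and inflammation". Section 7.1.2 lists the biomarkers that serve it. The list includes "tissue inhibitor of metalloproteinases-1 (and derived enhanced liver fibrosis score), Pro-C3", with change assessed "from baseline to Week 4, Week 8, and Week 14/ET, as applicable". Section 10.2.1.3 sets the method: "secondary efficacy variables measured at multiple timepoints will be analyzed by mixed effect model repeated measures model". It makes no exception for ELF.

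**SAP.** Section 2.1.2 keeps ELF in the endpoint table for the same objective: "tissue inhibitor of metalloproteinases-1 (and derived enhanced liver fibrosis [ELF] score" (the closing bracket follows in the source). Section 3.4.2 opens by saying that the remaining secondary efficacy endpoints are both described and analysed on the ITT Population. Section 3.4.2.1 gives an MMRM for change in the available biomarkers, with LSMeans compared between treatment groups at each post-baseline visit. It then closes with: "The derived noninvasive biomarkers, including ELF, will be summarized only. No formal statistical analysis will be conducted".

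Section 5 introduces its shorter list of departures with "There are some other minor changes from the protocol-specified statistical analyses detailed in this SAP". That list covers the added Week 12 biomarker visit, ET assessments and HbA1c timing. ELF is not in it.

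**The concern.** A protocol-named secondary endpoint loses its protocol-assigned between-group analysis. The sentence responsible conflicts with the protocol and with the SAP's own general statement in 3.4.2, and no reason is given.

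At stake is how the fifth secondary objective can be reported. The individual markers will come with adjusted treatment differences, but the score that the protocol lists beside them will not. If the gap is noticed only after unblinding, any ELF comparison becomes post hoc, although the protocol had planned one.

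**Working it through.** **1. The texts side by side**

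| Place | Treatment of ELF |
|---|---|
| Protocol 7.1.2 | Secondary efficacy variable; Weeks 4, 8 and 14/ET |
| Protocol 10.2.1.3 | Falls under the MMRM rule |
| SAP 2.1.2 | Retained as an endpoint for the fifth secondary objective |
| SAP 3.4.2 | To be described and analysed, like the other secondary endpoints |
| SAP 3.4.2.1 | Described only |
| SAP 5 | No entry |

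**2. Does being a calculated score explain it?** Not by itself. The AST/ALT ratio is also calculated, yet the SAP gives it its own baseline rule (3.1.3) and visit windows (3.1.4) and does not place it among the derived scores in 2.1.2. The scores that are placed there (AST to platelet ratio index, BAAT, BARD, NAFLD Fibrosis Score, FIB-4) appear only in the SAP, so the protocol assigned them no model. ELF differs from them in that respect.

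**3. Contrasts affected in Part B.** Protocol 6.3.3 and 6.4 schedule fibrosis and inflammation sampling at Day 1 and then Days 28, 56 and 98. The Group III windows in SAP 3.1.4 give the same three post-baseline visits.
- Planned under the protocol rule: 2 doses × 3 visits = 6.
- On treatment (Weeks 4 and 8): 2 × 2 = 4.
- Off treatment (Week 14): 2 × 1 = 2. Day 98 is 98 − 84 = 14 days after the end of treatment.
- Planned under SAP 3.4.2.1: 0 of 6.

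**4. What remains.** SAP 3.4.2 provides descriptive statistics by group for baseline, visit value and change. A reader could therefore form a crude ELF difference. It would not be adjusted for baseline or stratification factors and would not use the repeated-measures structure.

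**5. Precision of a restored comparison (orientation only).** The plan gives no figure for ELF, so the arm size is taken from the primary endpoint in Protocol 10.2.8 (difference 5.1, SD 5.8, one-sided alpha 0.0125, power 0.80).
- Z formula: n = 2 × [(2.2414 + 0.8416) × 5.8 / 5.1]² = 24.59, so 25 against the stated 26.
- The t-test version gives power 0.784 at 25 and 0.802 at 26, so it returns 26.
- Dropout: 26 / (1 − 0.13) = 29.9, so 30 randomized, as stated.

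The documents give no SD for ELF change, so the following are in SD units, unadjusted, per dose versus placebo:

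| Per arm | SE = √(2/n) | 95% CI half-width = 1.96 × SE | Detectable at 80% power, one-sided 0.025 = (1.960 + 0.842) × SE |
|---|---|---|---|
| 26 | 0.277 | 0.54 | 0.78 |
| 30 | 0.258 | 0.51 | 0.72 |

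The comparison would be imprecise, but at the same arm size and on the same scale this holds equally for the biomarkers that the SAP does model.

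**The case against.** The strongest case for leaving the SAP alone has four parts.

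- **The choice is on record.** SAP 3.4.2.1 names ELF and says openly that it will not be tested. A reader might infer that the analysis was dropped silently, and the documents do not support that. What is missing is its declaration as a change from the protocol. Section 5 is also not a complete log: it omits the Part B move of hs-CRP to a Wilcoxon analysis. But hs-CRP keeps a between-group estimate and interval (Hodges-Lehmann), whereas ELF keeps neither.
- **Information on ELF and on fibrosis is not lost.** A reader might infer that the trial will say nothing about ELF, or that the fifth secondary objective goes untested. Neither follows. By-group ELF changes are tabulated (SAP 3.4.2), the available individual biomarkers are compared by MMRM (3.4.2.1), and cT1 has its own ANCOVA with multiple imputation (3.4.1.5). This part of the objection stands, and it limits the point to the adjusted ELF contrast.
- **The ELF formula is not in the documents.** SAP 3.4.2.1 sends it to separate specifications, so its components cannot be confirmed here. This does not affect the remedy: the SAP already plans to derive ELF and summarise it by visit, so the values an MMRM needs will exist.
- **One more nominal test on a long list adds little.** Keeping a derived score descriptive is defensible. But that is an argument for declaring the choice with its reason, and the SAP does neither.

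**Conclusion.** The inconsistency is real and limited in size. SAP 3.4.2.1 removes the MMRM comparison that Protocol 10.2.1.3 assigns to ELF, contradicts SAP 3.4.2, and is not declared in SAP Section 5. In Part B, 6 adjusted contrasts are not planned, 4 of them on treatment. The primary LFC analysis, its alpha and the sample size do not change.

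A reader might go further and say that the trial's only composite fibrosis marker goes unestimated. The documents do not support that: the SAP adds other composite scores, and crude ELF differences can be read from the summaries. ELF is the only composite on the protocol's own list, and then only if the AST/ALT ratio is taken as a simple ratio.

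The conclusion rests on reading the protocol's MMRM rule as covering every repeatedly measured variable in Section 7.1.2, which its wording does. It is worth correcting before the first database lock, when SAP 4.2 unblinds the sponsor and the biostatistics team.

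**What to change.** **Preferred.** In SAP 3.4.2.1, limit the summary-only rule explicitly to derived biomarkers other than ELF. Merely deleting the mention of ELF would not be enough, because both documents call ELF derived and the sentence could still be read as covering it. Then state that change in ELF will be analysed with the MMRM already given in that section, using baseline ELF as the baseline value:
- Part B: each dose versus placebo, with statin use and LFC category as stratification factors.
- Part A, if re-run: pooled EYP001a versus placebo, with statin use and T2DM status.

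Report LSMean differences with 95% CIs at each visit, labelled as nominal secondary results, and mark Week 14 as off treatment. The scores introduced by the SAP can stay descriptive.

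**Alternative.** If the sponsor keeps ELF descriptive, declare the departure from Protocol 10.2.1.3 in SAP Section 5 with a reason, and align SAP 3.4.2 with it, before the first database lock.

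**Cost.** One reworded sentence, one sentence of model specification and one table. No new samples or visits are needed. The downside is one more set of nominal comparisons without multiplicity adjustment.

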3.4.2.2 Liver Stiffness Measurements (LSM, VCTE)

The change and percent change from baseline to Week 12/ET in FibroScan results (LSM and VCTE) will be analyzed for the ITT Population using ANCOVA models with baseline LSM as a

covariate and treatment (pooled EYP001a and placebo) and stratification factors – statin use and T2DM status at screening as factors.

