2.2 Study Design

2.2.1 Overview

This is a 2-part, randomized, double-blind, multicenter, placebo-controlled study to evaluate the safety and efficacy of EYP001a in patients with NASH who likely have stage F2 to F3 fibrosis at approximately 50 global clinical sites. Overall, approximately 114 eligible patients will be enrolled: 24 patients in Part A (Safety Run-in Cohort), followed by 90 patients in Part B. In Part A, 24 patients will be randomized on Day 1 to 1 of 4 parallel treatment groups: 100 mg EYP001a twice daily (BID), 200 mg EYP001a once daily (QD), 400 mg EYP001a QD, or placebo BID. In Part B, 90 patients will be randomized on Day 1 to 1 of 3 parallel treatment groups: 100 mg EYP001a QD, 200 mg EYP001a QD, or placebo QD.

Randomization will be stratified by statin use (yes, no) and type 2 diabetes mellitus (T2DM) status (yes, no) at screening in Part A, and by statin use (yes, no) and LFC (stratification factor with 3 categories: LFC<16%, 16%≤LFC<22%, and 22%≤LFC) in Part B at screening.

BID = twice daily; D = Day; DSMC = Data Safety Monitoring Committee; QD = once daily; Wk = Week.

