3 STATISTICAL METHODOLOGY

3.1 General Considerations

3.1.1 Treatment Groups

Data will be summarized and listed according to the randomized or actual treatment group, as appropriate.

In addition for Part A, data from the EYP001a treatment groups will be pooled and summarized. For analysis, due to the small number of patients by treatment group and as the PK results between group were found to be non-linear, with similar exposure for the EYP001a 200 mg QD and EYP001a 400 mg QD groups, only the pooled EYP001a treatment group will be compared with placebo.

In Part B, treatment groups will be summarized and analyzed separately. The EYP001a treatment groups will not be pooled.

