4.2 Pre-final Analysis

Part A: After the database is frozen and exclusions from analysis populations have been finalized, the Part A randomized treatment assignments will be unblinded and the Part A pre-final analysis will be generated.

Part B: Database lock and analysis will occur in two steps as described below. The purpose of conducting the database lock and analysis in two steps is to obtain the primary analysis results of the 12-week treatment period as soon as possible for corporate goals. The trigger for the first step database lock is when the last patient finishes Week 12. Patients will no longer be on treatment for the remainder of the study follow-up period, therefore it is not considered to be a substantial risk to the patients or study data to conduct the primary analysis prior to the final database lock.

1. First step: efficacy analyses up to Week 12 - This analysis will be conducted on all randomized patients when all patients will have all their MRI-PDFF, cT1, and laboratory data up to the Week 12 analysis window collected and validated (i.e. SDV'd, reconciled, and locked). The efficacy analyses will be performed up to the Week 12 time point. In other words, the Analysis Data Model (ADaM) efficacy datasets will only include data through Week 12.

Analyses of MRI-PDFF and cT1 endpoints up to the Week 12 time point will correspond to the final analyses for these endpoints. Any other analyses using MMRM, such as laboratory data, up to the Week 12 time point will not exactly correspond to the final analyses for these endpoints. This is because the analysis model is MMRM and includes

Week 14 time points in the model, which will not be included for the first step database lock. After the final database lock when all Week 14 data is available and added to the MMRM, results for all visits used in the MMRM may change.

The efficacy data to be analyzed up to Week 12 includes MRI-PDFF, cT1, LSM, ALT, LDL-C, and body weight.

The safety analyses will be performed on all safety data collected up to the common cut-off date. For this analysis, the common cut-off date is defined as the date of the first database lock that occurs after the last Week 12 visit. The safety analysis will be updated after the second step database lock.

The safety data to be analyzed includes adverse events and GGT.

Summaries of demographics and disposition will also be provided.

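### SAP 3.4.2.2 gives only the Part A model for liver stiffness; applied to Part B it conflicts with the no-pooling rule, treats T2DM as a stratification factor and omits the LFC stratum

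*SAP*

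**What the plan says.** SAP 3.4.2.2 opens: "The change and percent change from baseline to Week 12/ET in FibroScan results (LSM and VCTE) will be analyzed for the ITT Population". The model is ANCOVA with baseline LSM as "covariate and treatment (pooled EYP001a and placebo) and stratification factors", those factors being statin use and T2DM status at screening. It makes no distinction between Part A and Part B.

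The general rules do distinguish them. For Part A, SAP 3.1.1 says that "only the pooled EYP001a treatment group will be compared with placebo". For Part B it says: "In Part B, treatment groups will be summarized and analyzed separately. The EYP001a treatment groups will not be pooled". SAP 2.2.1 states that randomisation was stratified by statin use and T2DM status in Part A, and "by statin use (yes, no) and LFC (stratification factor with 3 categories: LFC<16%, 16%≤LFC<22%, and 22%≤LFC) in Part B at screening".

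LSM is within the Part B analysis. SAP 3.1.4 assigns visits for LSM under its Part B heading. SAP 4.2, describing the Part B first-step lock, says: "The efficacy data to be analyzed up to Week 12 includes MRI-PDFF, cT1, LSM, ALT, LDL-C, and body weight".

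**The concern.** The SAP's introduction says that this version concentrates on what Part B needs, yet the only model with LSM as the outcome is the one for Part A. A programmer following 3.4.2.2 for Part B would break 3.1.1. A programmer following 3.1.1 would still have no stated set of factors for this model.

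At stake is an LSM result in the Part B first-step output that answers a different question from the other outcomes in that output: an average over 100 mg and 200 mg instead of each dose against placebo. Under SAP 4.2 the sponsor and the biostatistics team are unblinded at the first-step lock, and topline outputs follow about a week later. If the conflict is not settled before that lock, the contrast and the factors could be chosen with treatment codes known.

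**Working it through.** The documents give no sample size, effect or standard deviation for LSM, so there is no stated figure to reproduce. The check is a comparison of texts, followed by a count of what the model would estimate.

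**1. The LSM model against the Part B rules**

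| Element | SAP 3.4.2.2 | Part B rule | Match |
|---|---|---|---|
| Treatment | Pooled EYP001a vs placebo | Doses analysed separately (3.1.1) | No |
| Statin use | Included | Stratification factor (2.2.1) | Yes |
| T2DM | Included as a stratification factor | Not a stratification factor (2.2.1) | No |
| LFC category, 3 levels | Absent | Stratification factor (2.2.1) | No |
| Baseline LSM | Covariate | Suits an LSM outcome | Yes |

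**2. Is there another LSM model?** No. In SAP 3.4.1.1, LSM and CAP appear only as added covariates in the LFC model. SAP 5, which lists changes from the protocol, does not mention LSM.

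**3. Does it look deliberate?** Sections 3.4.2.1, 3.4.2.3 and 3.4.2.5 each give separate Part A and Part B treatment terms and factors, and 3.4.2.4 is written for Part B alone. Section 3.4.2.2 is the only one of the five with Part A wording and nothing else. This looks like carry-over.

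**4. Would the LFC stratum be wanted here?** By the SAP's own reasoning, yes. SAP 5 drops it from the LFC models because baseline LFC is already a covariate. SAP 3.4.1.5 keeps it for cT1, where baseline cT1 replaces baseline LFC. An LSM model with baseline LSM is in the same position as cT1.

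**5. Could T2DM be programmed as a Part B stratification factor?** Not as specified. SAP 3.3.4 takes stratification variables from the values used at randomisation and lists T2DM for Part A only.

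**6. What the model would estimate in Part B** (30 randomised per arm, from SAP 2.2.4; all assumed measured; standard errors in units of the residual SD, ignoring covariates)

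- As written: 1 contrast, 60 vs 30. SE = √(1/60 + 1/30) = 0.224. Parameters: intercept 1 + treatment 1 + statin 1 + T2DM 1 + baseline 1 = 5. Residual df = 90 − 5 = 85.
- With the Part B terms: 2 contrasts, 30 vs 30 each. SE = √(1/30 + 1/30) = 0.258. Parameters: intercept 1 + treatment 2 + statin 1 + LFC category 2 + baseline 1 = 7. Residual df = 90 − 7 = 83.

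The dose-specific SE is 0.258/0.224 = 1.15 times the pooled one. With equal numbers measured, the pooled contrast is the simple average of the two dose effects. Because the Week 12 FibroScan is optional, actual numbers may be smaller and unequal.

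**The case against.** The best reply is that the rest of the plan already settles most of this. SAP 3.1.1 forbids pooling in Part B, and SAP 3.4.2 presents descriptive statistics by treatment group for each secondary efficacy parameter. Protocol 10.2.1.3 calls for an ANCOVA similar to the primary one for secondary changes to Week 12, and the primary model in Protocol 10.2.1.1 uses statin use and LFC category in Part B. LSM is also a minor variable: it is not in the secondary lists of Protocol 7.1.2 or SAP 2.1, and the Week 12 and early termination FibroScans are optional in Protocol 6.3.3.7 and 6.5.

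Much of that stands, and it limits the weight of the point. It does not remove it. SAP 3.1.1 settles the pooling but not the factors. The protocol's similar-model rule covers secondary efficacy variables, and LSM is not listed as one. The explicit text of 3.4.2.2 still says something else.

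Several stronger readings are tempting but not supported:

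- A reader might infer that Part B will have no LSM result by dose. That is true only of this model; the descriptive summaries by treatment group remain.
- A reader might infer that the randomisation factors are wrong throughout. Statin use is right; one factor is misplaced and one is missing. Adjusting for T2DM, a baseline characteristic, is not in itself biasing. The error is to call it a Part B stratification factor.
- A reader might want to state how far a pooled estimate would miss each dose's effect. That needs an assumed dose-response for LSM, and the documents give none.
- A reader might infer that a CAP model has been lost. The SAP defines a baseline and visits for CAP but nowhere plans an inferential analysis of it as an outcome. Adding one would be a new analysis, not a correction.

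**Conclusion.** The point holds as an internal contradiction and a gap in specification. For Part B, SAP 3.4.2.2 conflicts with 3.1.1 on pooling, names one stratification factor that does not apply and omits one that does. Run literally, it gives one pooled contrast where the Part B design calls for two.

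The impact is modest. The primary LFC analysis and the sample size are untouched, and the affected result is an optional measurement outside the listed secondary efficacy variables. The SAP should still be corrected, because LSM is named for the first-step output and no other text supplies its Part B factors. The conclusion assumes that its place in that list means the 3.4.2.2 model is to be run in Part B. If only a descriptive summary is intended, the SAP should say so, and the conflict disappears.

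**What to change.** Limit the present paragraph of SAP 3.4.2.2 to Part A. Add for Part B: ANCOVA of change and percent change in LSM from baseline to Week 12/ET, with treatment (each EYP001a dose versus placebo), statin use and LFC stratification category as factors and baseline LSM as covariate. This is the factor structure of the cT1 model in 3.4.1.5. The parallel covers the factors only; it need not import that section's multiple imputation, since SAP 3.1.9 leaves missing values unreplaced unless stated otherwise. Reword the outcome as LSM by VCTE.

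The cost is one paragraph of SAP text and a small programming change, with no new data. The dose contrasts will be about 15% less precise than a pooled one (SE ratio 1.15), which is the price of estimating each dose separately. The change should be made before the first-step lock or, if that has passed, documented in the clinical study report as SAP 1 provides for deviations.
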